5.4.2.2 ATIMP Administration Procedures

The protocol describes the intended surgical technique for ATIMP administration. The surgical procedure may be modified on a case-by-case basis in the interests of safety: any modification will be documented in the operation notes and CRF. Consent to record the surgery will be requested of the participant. Intraocular surgery will be recorded using a video camera via the operating microscope as described in the consent process. Relevant recordings and images will be stored alongside the trial database.

5.4.2.2.1 Pre-operative procedure

For prophylaxis against potential intraocular immune responses to the ATIMP, participants will be prescribed a course of daily oral prednisolone commencing at a dose of 30mg daily for one week prior to ATIMP administration.

Preoperative procedures and intraocular administration of ATIMP will be as described in the Gene Therapy for X linked RPGR Study Manual.

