4.3.2.2.5 Confirmatory Safety Phase

The adult dose escalation component of the study is complete at the time of protocol amendment v9.0. Review of the data collected to date with the IDMC led to a decision not to pursue the higher dose level and to commence administration for confirmation in paediatrics at the intermediate dose level. Children are defined as those aged 15 and under in the UK, and 17 and under in the US. These participants in the paediatric confirmation phase are administered the intermediate dose

been shown to be well tolerated in adults. Having identified children who may be willing to participate in the study, the CI will prioritise ATIMP administration to older candidates in the 1st instance. The 1st child administered ATIMP will be monitored for safety for a period of 4 weeks. If there is no adverse event consistent with the above definition of a DLE after 4 weeks, ATIMP will be administered to further children.

In order to fully explore dose levels and make optimal use of the expansion phase of the study, a treatment group randomisation will subsequently occur to either low or intermediate dose; to achieve up to 32 participants receiving intervention at baseline, and up to 16 further participants receiving deferred intervention at 6 months following baseline (control group). The expansion phase will include up to 48 participants in total, who may be adults or children.

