5.3.1.2 Participant Inclusion Criteria

Inclusion in the trial will be limited to individuals who meet the following criteria:

- 1. Are males aged 5 years or older
- Have X-linked retinitis pigmentosa confirmed by a retinal specialist (CI or PI)
- Have relatively symmetrical retinal disease both structurally and functionally defined as < 15
 letters [Best Corrected Visual Acuity (BCVA)] difference between eyes
- 4. Have a predicted disease-causing missense or null mutation in *RPGR* confirmed in an accredited laboratory
- 5. Evidence of relative preservation of retinal structure at the macula

- 6. Evidence of impaired navigation in dim illumination on Mobility assessment in **both** eyes monocularly; defined by either an inability to complete the visual mobility maze at the 1 lux level, or the time taken to complete the maze at either 1 or 4 lux being greater or equal to 12 seconds.
- 7. Are able to give informed consent or assent, with the guidance of their parent/guardian where appropriate: children aged 5-6 years will not be asked to provide assent
- 8. Are able to undertake age appropriate clinical assessments at the trial sites as specified in the protocol
- 9. Are willing to use barrier and spermicide form of contraception or will be sexually abstinent (when this is in line with the participant's preferred and usual lifestyle) for at least 12 months following ATIMP administration
- 10. Are willing to give consent for the use of blood and blood components collected through the trial for the investigation of immune responses to the ATIMP

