5.4.1.6 Name and Description of Each Non-Investigational Medicinal Product (NIMP)

- 1. Cefuroxime can be administered subconjuctivally at 50mg in 0.5ml normal saline, or 125mg in 1.0mL normal saline according to local practice. or cefazolin at 50 mg/0.5mL or vancomycin at 25 mg/0.5 mL antibiotic given at usual dose at end of surgery (standard (as per British National Formulary) dose as prophylaxis for post-operative infection) or any other antibiotic prescribed as per local hospital practices.
- 2. Long acting steroid in the sub-tenon space following sclerotomy closure according to local guidelines/standard of care.
- 3. Betamethasone can be administered subconjunctivally at 2mg 5mg in 0.5mL, according to local practice. or dexamethasone can be administered subconjunctivally at 1.5mg- 2.0mg in 0.5mL, according to local practice.at end of surgery (standard dose as prophylaxis for post-operative inflammation)) or any other steroid prescribed as per local hospital practices.
- 4. Chloramphenicol 0.5% or ofloxacin (topical antibiotic) 4 times daily for 7 days following ATIMP administration.
- 5. Dexamethasone 0.1% (topical steroid) or topical prednisolone drops 1.0% should be administered 4 times daily for 4 weeks, then 2 times daily for a further 2 weeks (weeks 4 to 6) following ATIMP administration.
 - 3and 4 above will be administered to minimise inflammation and protect against infection postoperatively.

6. Omeprazole:

- In adults 20mg per day for the duration of the steroid treatment
- In children aged up to 16 weighing 5 kg to less than 10 kg (11 lb to less than 22 lb): 5 mg taken once per day for the duration of the steroid treatment
- In children aged up to 16 weighing 10 kg to less than 20 kg (22 lb to less than 44 lb): 10 mg taken once per day for the duration of the steroid treatment
- In children aged up to16 weighing 20 kg (44 lb) or more: 20 mg taken once per day for the duration of the steroid treatment
- 7. Prednisolone or Prednisone (oral steroid) as prophylaxis against potential intraocular immune responses:

For adults 30 mg daily for one week **prior** to ATIMP administration Following the ATIMP administration as follows:

- 60 mg daily in week 1
- 40 mg daily in week 2
- 30 mg daily in week 3
- 20 mg daily in week 4
- 15 mg daily in week 5
- 10 mg daily in week 6
- 5 mg daily in week 7
- 2.5 mg daily in week 8

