Children will be prescribed a tapering regimen of prednisolone tailored according to age and weight, and in addition intravenous methylprednisolone 30mg/kg on the day of surgery (maximum total no more than 1g). A further dose of methylprednisolone may be administered at week 4 in the presence of signs of intraocular inflammation. The regimen is described below:

- 0.5 mg/kg daily for one week **prior** to ATIMP administration
- 1 mg/kg daily for the first week following ATIMP administration
- 0.8 mg/kg daily for the second week following ATIMP administration
- 0.7 mg/kg daily for the third week following ATIMP administration
- 0.6 mg/kg daily for the fourth week following ATIMP administration
- 0.5 mg/kg daily for the fifth week following ATIMP administration
- 0.4 mg/kg daily for the sixth week following ATIMP administration
- 0.25 mg/kg daily for the seventh week following ATIMP administration
- 0.125 mg/kg daily for the eighth week following ATIMP administration

•

Following completion of steroid treatment, testing (if required), will be performed to confirm Hepatitis B viral load.

All Non-Investigational Medicinal Products (NIMPs) are licensed within the EU and US and will be procured from standard hospital stock.

Sites will maintain a system that allows adequate reconstruction of NIMP movements and permits recording of which participants received which NIMPs during the trial, with an evaluation of compliance where necessary.

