5.4.2.3 Subsequent Assessments

On the 1st postoperative day, a full clinical ocular examination will be performed. Visual acuity, intraocular pressure, the degree of postoperative intraocular inflammation and the area of any residual retinal bleb will be documented. Fundus photography, ocular examination, intraocular pressure and SD-OCT will be performed at day 1 and each subsequent visit post ATIMP administration.

A standard post-vitrectomy treatment regimen of topical antibiotic (chloramphenicol 0.5% qds for 7 days) and steroid (dexamethasone 0.1% qds for 4 weeks and then bd for a further 2 weeks) will be prescribed to minimise inflammation and protect against infection postoperatively.

Intraocular pressure of greater than 30 mmHg will be managed with systemic therapy where indicated with specialist advice sought as required.

Participants will be maintained on oral prednisolone (or other as appropriate) for 8 weeks following administration of ATIMP as described above (Section 5.4.2.2.1: Pre-operative procedure). The possible development of steroid-induced adverse effects will be monitored regularly. In particular, blood pressure will be measured, and blood glucose, renal function and liver function will be evaluated through blood biochemistry at the time points specific in Table 3, Trial Assessments (Dose Escalation Phase, Paediatric Dose Confirmation Phase, and Immediate Treatment Arms of Dose Expansion Phase) and Table 4: Trial assessments (Deferred Treatment Group)

Both safety and efficacy of the ATIMP will be evaluated at various time points up to 12 months after ATIMP delivery. Evaluations will comprise primarily ocular assessments. The nature and schedule (Section 5.6: Trial Assessments) of these is described below.

(i) Clinical assessment of intraocular inflammation

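### Protocol 5.4.2.2.1 sets a flat 30 mg daily pre-operative prednisolone dose for all participants, while 5.4.1.6 reserves 30 mg for adults and gives children 0.5 mg/kg in the same week

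*Protocol*

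**What the plan says.** Section 5.4.2.2.1 of the protocol (Pre-operative procedure) prescribes daily oral prednisolone to participants as prophylaxis against intraocular immune responses, "commencing at a dose of 30mg daily for one week prior to ATIMP administration". It sets no age limit, offers no paediatric alternative and does not point to 5.4.1.6. It then refers to the Study Manual for pre-operative procedures.

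Section 5.4.1.6 (non-investigational products) covers the same drug and the same week, but separates the two groups:

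- Adults: "For adults 30 mg daily for one week" before administration, followed by a fixed taper over 8 weeks.
- Children: "0.5 mg/kg daily for one week" before administration, then "1 mg/kg daily for the first week following ATIMP administration", tapering to week 8. Intravenous methylprednisolone is added on the day of surgery.

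Children are within scope. Inclusion criterion 1 reads "Are males aged 5 years or older". Section 4.3.2 allows up to 5 children in the paediatric confirmation phase, and section 4.3.2.2.5 opens the expansion phase to up to 48 participants "who may be adults or children".

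For the 8-week post-operative course, section 5.4.2.3 sends the reader back to the pre-operative section: "as described above (Section 5.4.2.2.1: Pre-operative procedure". That section contains no taper; the schedules are in 5.4.1.6.

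**The concern.** For a child in the pre-operative week, the protocol gives two doses and does not say which one governs. Section 5.4.2.2.1 is where a site would naturally look for the pre-operative instruction. Section 5.2 requires sites to comply with the protocol and to document and explain deviations. As written, either dose given to a child (other than one weighing 60 kg) departs from one of the two sections.

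What is at stake is paediatric exposure to a systemic steroid. Section 4.1.5.6 lists raised blood pressure and blood sugar, mood or behaviour change and increased infection risk among the possible effects of short-term use, and section 4.1.5 commits to limiting the risks to children. If the flat dose were followed literally, a child below 60 kg would receive more than the paediatric schedule intends, with the largest excess in the lightest children. No endpoint, sample size or analysis depends on this.

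**Working it through.** **Inputs**

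- Flat dose: 30 mg/day for 7 days (5.4.2.2.1).
- Paediatric dose for the same week: 0.5 mg/kg/day for 7 days (5.4.1.6).
- Highest daily oral dose in the paediatric schedule: 1 mg/kg, in the first post-operative week (5.4.1.6).
- Body weight *w*: not given in the documents. The values below are assumptions chosen to show the range.

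**Where the rules agree**

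0.5 × *w* = 30 gives *w* = 60 kg. Below 60 kg the flat dose is higher than the paediatric dose; above 60 kg it is lower.

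**Where the flat dose passes the paediatric oral peak**

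30 / *w* > 1 mg/kg when *w* < 30 kg.

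**Size of the gap**

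- Paediatric dose = 0.5 × *w*
- Flat dose per kg = 30 / *w*
- Ratio = 30 / (0.5 × *w*)
- Difference over the week = 7 × (30 − 0.5 × *w*)

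| Assumed weight | Paediatric dose (mg/day) | Flat dose (mg/kg) | Ratio | Difference over 7 days (mg) |
|---|---|---|---|---|
| 15 kg | 7.5 | 2.0 | 4.0 | 157.5 |
| 20 kg | 10 | 1.5 | 3.0 | 140 |
| 30 kg | 15 | 1.0 | 2.0 | 105 |
| 40 kg | 20 | 0.75 | 1.5 | 70 |
| 60 kg | 30 | 0.5 | 1.0 | 0 |
| 70 kg | 35 | 0.43 | 0.86 | −35 |

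**Against the whole planned course**

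The paediatric oral doses sum to 0.5 + 1 + 0.8 + 0.7 + 0.6 + 0.5 + 0.4 + 0.25 + 0.125 = 4.875 mg/kg/day across nine weekly steps. Over 7 days each, that is 7 × 4.875 = 34.1 mg/kg, or about 683 mg at 20 kg. An excess of 140 mg is then 140 / 683, about 20% of the planned oral total. The single intravenous methylprednisolone dose on the day of surgery is 30 mg/kg, or 600 mg at 20 kg (a different drug, so the milligrams are not directly comparable).

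**The cross-reference**

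The pointer in 5.4.2.3 leads to a section without a post-operative schedule. A reader would find nothing to follow there, so this does not by itself produce a wrong post-operative dose. The dosing conflict is confined to the one pre-operative week.

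**The case against.** The strongest reply is that 5.4.1.6 is the dosing section and its specific paediatric rule would be understood to govern. Section 5.4.2.2.1 is a brief summary that leaves out the taper, omeprazole and the paediatric intravenous steroid, so nobody could prescribe the full course from it, and it defers to a Study Manual not available here. This probably describes the intention, and it lowers the likelihood of harm. But the summary is complete for the one thing in dispute, the dose in the pre-operative week. It states that dose itself before mentioning the manual, and no order of precedence is given.

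A second reply is that few children are exposed, and probably not the lightest. SAP section 1.2 describes the expansion phase as adult, and SAP section 1.4 mentions 3 paediatric participants, although the estimand in SAP section 5.3.2 still covers ages 5 and above. Protocol section 4.3.2.2.5 gives priority to older children in the paediatric phase, and section 5.4.2.3 requires reliable acuity, static field and mobility testing. The omeprazole list does include a band for lighter children ("In children aged up to 16 weighing 10 kg to less than 20 kg"), but it also has a 5 to under 10 kg band, which looks generic for a trial that starts at age 5. It is therefore weak evidence of the weights expected. These points stand: the 4-fold and 3-fold figures are the upper end of an assumed range.

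Third, the extra oral steroid is modest beside the planned course, and section 4.1.5.6 specifies monitoring for steroid effects. That is fair as context, but it does not make two conflicting instructions acceptable.

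Finally, the amendment log in this protocol ends at version 11.0, while the SAP is based on version 12.0. Whether the later version corrected the sentence cannot be determined from these documents.

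**Conclusion.** The contradiction is real and sits in current protocol text: 30 mg daily for participants generally in one section, and 30 mg for adults with 0.5 mg/kg for children in another. The flat dose is above the paediatric dose below 60 kg (3 times at an assumed 20 kg, 2 times at 30 kg) and above the paediatric oral peak below 30 kg. Above 60 kg the error runs the other way and is small.

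The multiples rest on assumed weights. The documents do not show that any child received the wrong dose, and a careful prescriber would probably have used 5.4.1.6. This is an inconsistency in the dosing text with paediatric safety relevance; it has no consequence for the statistical analysis. It should be corrected because the population is vulnerable and the correction is trivial. The wrong cross-reference in 5.4.2.3 is a minor tidying point and adds no weight.

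**What to change.** - In 5.4.2.2.1, limit 30 mg daily to adults and refer children to the 0.5 mg/kg schedule in 5.4.1.6. Alternatively, remove the dose from 5.4.2.2.1 and refer to 5.4.1.6 for everyone.
- In 5.4.2.3, change the cross-reference for the post-operative course from 5.4.2.2.1 to 5.4.1.6.
- Confirm that the Study Manual carries the same adult and paediatric doses. If version 12.0 already makes these corrections, the sponsor need only say so.
- Section 5.4.7 requires steroids to be recorded in the CRF, so the sponsor can also check what treated children received in the pre-operative week.

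The cost is two wording corrections and a check of existing documents and records. Design, visits and analysis do not change.

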5.4.2.2.2 Operative procedure

In the dose escalation and dose confirmation in paediatric participants phases of the study, the choice of eye for ATIMP administration will be the poorer-seeing eye as identified by the participant and CI/PI taking account of ocular dominance and visual acuity. In the randomised expansion phase, the eye to be

administered vector will be determined via randomisation to preserve objectivity. In order for this to be safely performed participants are required to have relatively symmetrical visual acuity.

The recombinant vector will be delivered in the form of a suspension of viral vector particles injected intraocularly (subretinally) under direct observation using an operating microscope. This procedure will include a 3-port pars plana vitrectomy followed by injection of ATIMP using a fine cannula through small retinotomies into the subretinal space.

Surgery will be performed under general anaesthesia. The eye and face will be prepared using povidone iodine solution as per routine intraocular surgery. The face and eye will be covered with an adhesive sterile plastic drape. An opening will be made at the point of the palpebral fissure (when applicable) and a wire speculum inserted to retract the upper and lower eyelids. The speculum and all intraocular instruments will be sterilised according to standard local operating procedures. 3 pars plana sclerotomies will be sited to enable intraocular infusion, endoillumination probe and surgical instruments. The fundus will be viewed by means of a wide field indirect viewing system or a contact lens. To minimise the possibility of unplanned retinal detachment or preretinal fibrosis, vitrectomy (aspiration of vitreous gel) will be performed using a disposable cutter.

Intraocular administration of the viral vector suspension (AAV2/5-hRKp.RPGR) will be performed using a subretinal cannula advanced through the retina. Under direct visualisation, the ATIMP will be injected under the neurosensory retina, causing a localised retinal detachment with a self-sealing non-expanding retinotomy. If appropriate, the bleb of ATIMP will be manipulated to the target area using a fluid-air exchange. The site and extent of the subretinal bleb of ATIMP suspension will be documented by video recording.

Following intraocular administration of ATIMP, the retinal periphery will be examined for any unplanned retinal breaks for appropriate management by retinopexy with or without intraocular tamponade at the discretion of the operating surgeon. Intraocular instruments used subsequent to ATIMP delivery are disposable and will be destroyed after a single use. Sclerotomies may be secured using a vicryl suture. Standard doses of antibiotic and steroid will be administered subconjunctivally as prophylaxis against postoperative infection and inflammation respectively. Bupivacaine will be administered for analgesia.

The surgical procedure may be modified on a case-by-case basis in the interests of safety; any modification will be documented in the operation notes and CRF.

On the basis of experience, it is anticipated that the subretinal ATIMP bleb will resolve spontaneously during the first 48 hours.

Surgery may be performed, as is conventional for intra-ocular procedures, on a day-case basis and participants will be managed subsequently as out-patients, although hospital-based accommodation may be used for convenience.

5.4.2.3 Subsequent Assessments

On the 1st postoperative day, a full clinical ocular examination will be performed. Visual acuity, intraocular pressure, the degree of postoperative intraocular inflammation and the area of any residual retinal bleb will be documented. Fundus photography, ocular examination, intraocular pressure and SD-OCT will be performed at day 1 and each subsequent visit post ATIMP administration.

A standard post-vitrectomy treatment regimen of topical antibiotic (chloramphenicol 0.5% qds for 7 days) and steroid (dexamethasone 0.1% qds for 4 weeks and then bd for a further 2 weeks) will be prescribed to minimise inflammation and protect against infection postoperatively.

Intraocular pressure of greater than 30 mmHg will be managed with systemic therapy where indicated with specialist advice sought as required.

Participants will be maintained on oral prednisolone (or other as appropriate) for 8 weeks following administration of ATIMP as described above (Section 5.4.2.2.1: Pre-operative procedure). The possible development of steroid-induced adverse effects will be monitored regularly. In particular, blood pressure will be measured, and blood glucose, renal function and liver function will be evaluated through blood biochemistry at the time points specific in Table 3, Trial Assessments (Dose Escalation Phase, Paediatric Dose Confirmation Phase, and Immediate Treatment Arms of Dose Expansion Phase) and Table 4: Trial assessments (Deferred Treatment Group)

Both safety and efficacy of the ATIMP will be evaluated at various time points up to 12 months after ATIMP delivery. Evaluations will comprise primarily ocular assessments. The nature and schedule (Section 5.6: Trial Assessments) of these is described below.

(i) Clinical assessment of intraocular inflammation

The degree of intraocular inflammation will be assessed by slit-lamp biomicroscopy at each time point. A temporary intraocular inflammatory response is expected following vitrectomy surgery. This is typically evident clinically on slit-lamp biomicroscopy as 'flare' and cells in the anterior chamber and can be of moderate (2+ cells) intensity. The degree of intraocular inflammation is expected to decline over the course of the first 4 weeks following the surgical procedure, at which time the routine topical and systemic immunosuppression will be discontinued. Prolonged or severe intraocular inflammation, or deterioration in visual acuity that may be related to intraocular inflammation, will be investigated and managed conventionally with further topical and/or systemic immunosuppression.

(ii) Evaluation of immune responses

Up to 10 mL of blood will be collected to obtain serum samples to measure immune response. Antibody responses to AAV capsid proteins will be investigated by ELISA at baseline and at 4 weeks, 3 months and 6 months.

(iii) Evaluation of biodistribution

Systemic biodistribution of vector genomes will be assessed by PCR analysis of tears (a compressed cellulose sponge placed under the eye lid until swollen), saliva (a minimum of $100~\mu L$) and serum (1 mL) for patients in the immediate treatment arm at baseline 1, prior to intraocular ATIMP administration and day 1, week 1, week 2, week 4,week 6 and week 9 following intraocular ATIMP administration. For patients on the deferred treatment arm at baseline 1, month 6 prior to intraocular ATIMP administration and day 1, week 1, week 2, week 4, week 6 and week 9.

(iv) Assessment of visual function and retinal imaging

Assessment of visual function and retinal imaging will be performed as outlined in Section 5.6 (Trial Assessments). They will be carried out with the same methods applied for the baseline tests (see section 5.6 for details) to allow direct comparison of the data sets. These assessments will be scheduled over a period of a day for visits at day 1, day 3, day 7, week 2, week 4, week 6, and week 9 after surgery, and up

to 4 days for baseline examinations, and 3 months, 6 months, 9 months and 12 months following ATIMP administration. For the deferred treatment arm, assessments will be performed at day 1, day 3, day 7, week 2, week 4, week 6, week 9, month 3 and month 6 after surgery. For day 1 and 3, refraction cannot reliably be measured. Therefore, the most recent refraction measurement will be used.

All participants (adults and children) will need to be able to perform reliable visual acuity testing, SD-OCT, retinal sensitivity testing (static visual fields, and visual mobility assessment, which are the principal clinical assessments both for safety and efficacy. Other clinical assessments will be undertaken as appropriate for the ability of individual participants, since there is wide variation in the abilities of individual children to perform such tests reliably; the evaluations for individuals may be restricted to those tests that they are able to perform reliably.

Additional assessments may be performed if considered appropriate for the management of any unexpected adverse effects. These may be submitted as urgent safety measures and protocol amendments performed where required. Conversely, tests that cannot be reliably performed by a participant may be discontinued for that participant. This is not anticipated for the aforementioned key clinical assessments because participants who are unable to perform such tests will be excluded from the study at the screening phase. Evaluation of safety and efficacy will also be performed on an individual participant basis. We do not anticipate that any discontinuation will affect significantly the overall quality of the safety and efficacy evaluation.

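### Protocol 5.4.2.3(i) ends routine topical and systemic immunosuppression 4 weeks after surgery, while 5.4.2.3 and 5.4.1.6 run topical steroid to week 6 and oral steroid to week 8; the texts need reconciling

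*Protocol*

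**What the plan says.** Three places in the protocol set the length of routine steroid treatment after vector administration.

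- **5.4.2.3, part (i), on assessing intraocular inflammation.** Inflammation is expected to fall during the 4 weeks after surgery, "at which time the routine topical and systemic immunosuppression will be discontinued". The next sentence provides further topical or systemic immunosuppression for prolonged or severe inflammation.
- **5.4.2.3, opening paragraphs.** The topical regimen includes "steroid (dexamethasone 0.1% qds for 4 weeks and then bd for a further 2 weeks"). For the oral course: "Participants will be maintained on oral prednisolone (or other as appropriate) for 8 weeks following administration of ATIMP". That sentence sends the reader to 5.4.2.2.1 for the description.
- **5.4.1.6, items 5 and 7.** Topical steroid is given "4 times daily for 4 weeks, then 2 times daily for a further 2 weeks (weeks 4 to 6) following ATIMP administration". The adult oral taper is listed week by week and ends with "2.5 mg daily in week 8"; the paediatric taper also ends in the eighth week.

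The primary safety outcome (5.5.1) and the dose-limiting event (4.3.2.1) are both counted over the 9 weeks after administration, and severe unresponsive inflammation is a component of each.

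**The concern.** A reader of 5.4.2.3 meets a 6-week topical and an 8-week oral course, and then a statement that both kinds of routine treatment end at 4 weeks. All of this is current operative text.

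Two things are at stake. The first is conduct: this is the prophylaxis against intraocular immune responses, and sites could read its length differently. Other instructions are tied to the end of steroid treatment: the duration of omeprazole and the hepatitis B viral-load check (5.4.1.6), and the extra liver-enzyme monitoring (footnotes to Tables 3 and 4). The second is interpretation: SAP 6.1 tabulates ocular-inflammation events and summarises inflammation in cohorts before and after sub-Tenon triamcinolone was added. If background steroid duration varied for reasons of wording, that summary would be harder to read.

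**Working it through.** The plan states no figure to reproduce; the check is a side-by-side reading plus addition of durations. The starting points coincide, because the vector is given during the surgery (5.4.2.2.2), so weeks after surgery and weeks after administration are the same clock.

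| Source | Topical steroid ends | Oral steroid ends |
|---|---|---|
| 5.4.2.3(i) | week 4 | week 4 |
| 5.4.2.3, opening paragraphs | 4 + 2 = week 6 | week 8 |
| 5.4.1.6, item 5 | 4 + 2 = week 6 | – |
| 5.4.1.6, adult taper | – | week 8 |
| 5.4.1.6, paediatric taper | – | week 8 |

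**Size of the conflict.**
- Topical: 6 − 4 = 2 weeks.
- Oral: 8 − 4 = 4 weeks.
- Time off oral steroid inside the 9-week window: 9 − 8 = 1 week under the schedules, 9 − 4 = 5 weeks under 5.4.2.3(i).

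**Can the wording be read so that the conflict disappears?**
1. *As a step-down.* The topical schedule does drop from four to two applications a day at week 4. But 5.4.2.3(i) speaks of discontinuing, not reducing, and it covers systemic treatment as well.
2. *As a rule about rescue treatment.* It refers to the routine treatment, and deals with further immunosuppression separately in the sentence that follows.
3. *As superseded text.* The amendment history says version 3 lengthened the prophylactic course from 4 to 8 weeks. That suggests where a 4-week wording might have come from, but the sentence stands in the body of the present protocol. The conflict does not depend on the log, and I do not use the log to decide between durations.

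**Does the cross-reference settle it?** No. Section 5.4.2.2.1 describes only the week of oral prednisolone before administration and gives no postoperative course. A reader who follows the pointer does not reach the weekly taper, which is in 5.4.1.6.

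**The case against.** The strongest reply is that the ambiguity is small in practice. The prescribing text is explicit and agrees with itself: week-by-week tapers for adults and children in 5.4.1.6, with both durations restated in 5.4.2.3 shortly before the disputed clause. Monitoring for steroid effects runs to week 9 (4.1.5.6). The clause names no drug or dose and sits in a paragraph on the expected course of inflammation. A site would have to set aside a dated schedule to act on it. This stands, and it lowers the chance of divergent practice. It does not remove the contradiction, because the clause is still worded as an instruction covering both routes.

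A second reply is that the data to detect divergence are already collected. Protocol 5.4.7 requires steroids to be entered in the CRF, 5.4.1.6 requires sites to be able to show who received which non-investigational product, and SAP 4.5 presents corticosteroids among the medications of interest. This stands in full, so no new recording is called for.

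A third is timing. The SAP is based on protocol v12.0, while the amendment history here ends at v11.0, and the SAP describes expansion-phase randomisation and the deferred arm's crossover in the past tense. The sentence may have been changed, or a correction may come too late to alter treatment. Neither can be checked from these documents.

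A reader might also infer more than the text supports: that sites did stop at different times and that inflammation rates differed as a result. No document reports any site stopping at 4 weeks, and none gives a figure linking steroid duration to inflammation. The safety component is also narrower than inflammation in general. It requires grade 3+ cells, flare or haze that fails to improve by two steps, or to grade 0, over 6 weeks, and that is at least possibly related to the vector. Further immunosuppression is available for prolonged or severe inflammation whatever the routine course.

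**Conclusion.** The contradiction is real and rests on the wording alone: 2 weeks for topical steroid and 4 weeks for oral steroid, both inside the 9-week safety window. It is more than clerical, because it concerns prophylaxis in a first-stage gene therapy trial, touches the setting in which a primary safety component is assessed, and is compounded by a cross-reference that leads to no postoperative regimen.

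The consequence is a possibility only. Oral weeks 5 to 8 make up 4/9 = 44% of the window, but that is the share of the calendar on which the texts disagree. It measures neither bias nor any change in event rates. The conclusion assumes that the protocol text reviewed here was the one in force; v12.0 was not available. No view is taken on which duration is right.

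**What to change.** Reconcile 5.4.2.3(i) with the opening paragraphs of 5.4.2.3 and with 5.4.1.6, so that one duration is stated for topical and one for systemic treatment; the choice belongs to the sponsor and investigators. Correct the pointer from 5.4.2.3 to 5.4.2.2.1 so that it leads to a section containing the postoperative course. First check whether v12.0 already does this.

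If treatment is complete, the useful remainder is in reporting: show each participant's actual topical and oral steroid duration beside the ocular-inflammation tables in SAP 6.1. That would show whether the wording affected conduct.

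The cost is a protocol clarification and, if wanted, one listing from data already captured.
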